1.4 Study Design

[figure not shown]
This phase 2a study is a randomized, double-blind, placebo-controlled trial designed to assess the efficacy and safety of 13 once weekly doses of inhaled AZD1419 administered to patients with eosinophilic asthma controlled on a maintenance treatment of ICS plus a LABA but no other controller medication.

A withdrawal design will be used where the first 6 doses of IMP will be administered as add-on to the patient's regular ICS + LABA medication. The controller medication will then be tapered down and discontinued during the next 3 doses of IMP, and the last 4 doses will be administered during a period of complete ICS and LABA withdrawal (see [Figure 1](#)). In addition the study drug dose level will be adjusted using an adaptive dosing scheme (defined in [Section 4.2.2](#)) based on appearance of flu-like symptoms. The primary endpoint is loss of asthma control, defined in [Section 2.1.1](#). When a patient meets the primary endpoint the patient will resume ICS + LABA and will be followed for an additional 4 weeks before discontinuing the study.

The total duration of patient participation will be up to 56 weeks. This includes a screening period of approximately 2-4 weeks, a 12 week dosing period and an up to 40-week observation period following the last dose, further outlined in [Section 4](#). The schedule of trial procedures is presented in [Table 1](#).

The study will start with a sentinel dosing period to be conducted at 1 or 2 selected study centers, during which 4 patients will be randomly assigned 1:1 either to placebo or AZD1419 at 4 mg, dosed once weekly. Sentinel patients will be observed at the clinic for 24 hours after each of the first two doses, for details see [Section 4.2.1](#). A Data Safety Monitoring Board (DSMB) will review safety data from these patients and approve enrollment of additional patients in the study (details in [Section 6.8.1](#)).

Figure 1 Phase 2a Study Design

2. STUDY OBJECTIVES

2.1 Primary objective

Primary Objective:	Outcome Measure:
To assess the efficacy of inhaled AZD1419 in eosinophilic asthma patients after withdrawal of controller treatment of ICS + LABA	Time to loss of asthma control.

2.1.1 Definition of Loss of asthma control

For the purpose of the study Loss of asthma control is defined as any of the following:

- a) An increase of ACQ-5 to 1.5 or more
- b) A reduction of 30% or more in morning peak expiratory flow (PEF) from baseline on 2 consecutive days
- c) At least six additional reliever inhalations of SABA in a 24-hour period relative to baseline on 2 consecutive days
- d) An exacerbation requiring systemic corticosteroids

2.2 Secondary objectives

Secondary Objective:	Outcome Measure:
To further assess the efficacy of inhaled AZD1419 in eosinophilic asthma patients after withdrawal of controller treatment of ICS + LABA	Proportion of patients who experience loss of asthma control Changes over the course of the study in ACQ-5 Changes over the course of the study in asthma daily diary score Changes over the course of the study in number of moderate and severe exacerbations Changes over the course of the study in the use of reliever bronchodilator (short-acting beta-agonist SABA) Changes over the course of the study in pre- and post-bronchodilator FEV1 Changes over the course of the study in PEF Changes over the course of the study in fractional exhaled nitric oxide (FeNO)

2.3 Safety objectives

Safety Objective:	Outcome Measure :
To evaluate the safety and tolerability of AZD1419 in eosinophilic asthma patients after withdrawal of controller treatment of ICS + LABA	Adverse events, vital signs, ECG and laboratory parameters Weekly peak expiratory flow rate (PEFR) Lung diffusion capacity (DLco)

2.4 Exploratory objectives

Exploratory objective:	Outcome Measure:

 • To assess the responses of selected systemic peripheral blood and sputum biomarkers to inhaled AZD1419 in eosinophilic asthma patients after withdrawal of controller treatment of ICS + LABA • To assess the composite endpoint for exacerbations, CompEx • To investigate the genes and genetic variation that may influence response to AZD1419 • To assess the expression of selected genes in cells from whole blood and sputum • To assess the effects on DNA methylation • To assess the immune function of PBMC 	
 • Peripheral blood and sputum biomarkers (to be specified) • Time to first CompEx event • Changes over the course of the study in number of CompEx events • DNA • RNA from whole blood and sputum • DNA from whole blood • PBMCs

3. PATIENT SELECTION, ENROLMENT, RANDOMISATION, RESTRICTIONS, DISCONTINUATION AND WITHDRAWAL

Each patient should meet all of the inclusion criteria and none of the exclusion criteria for this study. Under no circumstances can there be exceptions to this rule.

3.1 Inclusion criteria

For inclusion in the study patients should fulfil the following criteria:

1. Provision of informed consent prior to any study specific procedures
2. Male and female patients 18 years and above
3. Physician-diagnosed asthma requiring treatment with ICS and a long-acting beta agonist (LABA), but no other controller medication. The ICS plus LABA can be

- any combination inhaler or 2 separate inhalers. Patients must have taken ICS plus LABA controller medication for at least 3 months prior to screening
4. Pre-bronchodilator forced expiratory volume in 1 second (FEV1) $\geq 50\%$ predicted
 5. Female patients must be 1 year post-menopausal, surgically sterile, or using an acceptable method of contraception, refer to Section 3.1.1.
 6. Negative pregnancy test (urine) and a date of last menstruation consistent with non-pregnancy for female patients of childbearing potential.
 7. Male patients must be surgically sterile or using an acceptable method of contraception (defined as barrier methods in conjunction with spermicides) from the first dose of the IMP and until 1 month after the last dose of the IMP to prevent pregnancy in a partner.
 8. Blood eosinophil levels ≥ 250 cells/ μL at screening OR a history of blood eosinophil levels ≥ 250 cells/ μL at any time in the preceding 2 years AND blood eosinophil levels ≥ 150 cells / μL at screening. The eosinophilia must be believed to be due to asthma and not have other known causes, e.g. helminth infection
 9. ACQ-5 score ≤ 1.5 at screening
 10. ACQ-5 score ≤ 0.75 at randomization
 11. Documentation of any of the following within 5 years prior to Visit 1:
 - Proof of post-bronchodilator reversibility in FEV1 of $\geq 12\%$ and ≥ 200 mL (Pellegrino et al 2005)
 - Proof of a positive response to a methacholine or histamine challenge (a decrease in FEV1 by 20% [PC20] at ≤ 8 mg/mL) performed according to ATS/ERS guidelines (American Thoracic Society 2000)
 - Proof of positive response to mannitol challenge (a decrease in FEV1 by 15% [PD15] at ≤ 635 mg or a $>10\%$ decrease in FEV1 between consecutive doses) (Anderson et al 2009)
 - Proof of diurnal variability in PEF $>20\%$ over the course of 24 hours in at least 4 out of 7 consecutive days

If historical documentation is not available, proof of reversibility or a positive response to a methacholine, histamine or mannitol challenge or diurnal variation must be demonstrated according to above and documented during Visit 1
 12. In the judgment of the investigator: able to adhere to study procedures including correct twice-daily use of the electronic symptom diary, home monitoring of peak flow, ability to perform spirometry and FeNO measurements
 13. Patients should be willing to switch to fixed dose morning and evening ICS+LABA in separate inhalers, together with SABA as rescue medication.

14. Patients who are blood donors should not donate blood during the study and for 3 months following their last dose of the IMP

In addition to the above, the following additional inclusion criterion will be applied to the Sputum Subset (approximately 20% of patients in selected sites)

15. Able to produce an adequate sputum sample at screening following induction with inhaled hypertonic saline

For inclusion in the genetic research, patients must fulfil all of the inclusion criteria above **and**:

16. Provide informed consent for the genetic sampling and analyses.

3.1.1 Acceptable birth control methods

Acceptable birth control methods are tubal occlusion, intrauterine device (provided coils are copper-banded), levonorgestrel intrauterine system (eg, Mirena™), medroxyprogesterone injections (eg, Depo-Provera™), etonogestrel implants (eg, Implanon™, Norplan™), normal and low dose combined oral pills, norelgestromin / ethinylestradiol transdermal system, intravaginal device (eg, ethinylestradiol and etonogestrel), desogestrel (eg, Cerazette™), total sexual abstinence and vasectomised sexual partner.

Women should have been stable on their chosen method of birth control for a minimum of 3 months before entering the trial and should continue with birth control for 1 month after the last dose of inhaled IMP. In addition to the acceptable birth control method (except for the practice of total sexual abstinence), condom should be used by male partner for sexual intercourse from randomization (Visit 2) and for 1 month after the last dose of inhaled AZD1419/matching placebo to prevent pregnancy.

The birth control method will be verified in the medical records prior to study start (contraceptive history) and women of childbearing potential will be asked to verify compliance at each visit up to 1 months after the last investigational product administration.

Patients should be made aware of the availability of emergency “post-coital” contraception if there is an indication for it (eg, missing IUD threads or a late injection). Acceptable emergency methods of contraception to be used should only include those approved by a regulatory agency in the patient’s region.

Women not of childbearing potential are defined as women who are either permanently sterilized (hysterectomy, bilateral oophorectomy, or bilateral salpingectomy), or who are postmenopausal. Women will be considered postmenopausal if they have been amenorrhoeic for 12 months prior to the planned date of randomization without an alternative medical cause. The following age specific requirements apply:

Women <50 years old would be considered postmenopausal if they have been amenorrheic for 12 months or more following cessation of exogenous hormonal treatment and follicle stimulating hormone (FSH) levels in the postmenopausal range.

Women \geq 50 years old would be considered postmenopausal if they have been amenorrheic for 12 months or more following cessation of all exogenous hormonal treatment

3.2 Exclusion criteria

Patients should not enter the study if any of the following exclusion criteria are fulfilled:

1. Clinically significant lung disease other than asthma (eg, chronic obstructive pulmonary disease, cystic fibrosis, allergic bronchopulmonary aspergillosis, active tuberculosis). Patients with CT or chest X-ray findings indicating bronchiectasis which in the opinion of the Investigator are not clinically significant may be enrolled at the discretion of the Investigator
2. Current tobacco smoking (smoking must have stopped for \geq 6 months prior to enrolment) or a history of tobacco smoking for \geq 10 pack-years (one pack year = 20 cigarettes smoked per day for 1 year)
3. Receipt of any marketed or investigational biologic within 4 months or 5 half-lives prior to enrolment (whichever is longer) or receipt of any investigational non-biologic agent within 30 days or 5 half-lives prior to enrolment (whichever is longer)
4. Known history of allergy or reaction to any component of the IMP formulation
5. Use of immunosuppressive medication (including but not limited to: methotrexate, troleandomycin, cyclosporine, azathioprine, systemic corticosteroids including regular treatment with OCS or intramuscular long-acting depot corticosteroids, or any experimental anti-inflammatory therapy) within 3 months prior to enrolment (Visit 1)
6. Receipt of immunoglobulin or blood products within 30 days prior to enrolment (Visit 1)
7. Positive HIV, hepatitis B surface antigen or hepatitis C virus antibody serology. Patients with a history of hepatitis B vaccination without a history of hepatitis B are allowed to be enrolled
8. History of autoimmune disease including but not limited to Wegener's granulomatosis, system lupus erythematosus, rheumatoid arthritis, Sjögren's syndrome, multiple sclerosis, autoimmune thrombocytopenia, primary biliary cirrhosis or any other autoimmune disease considered clinically relevant by the investigator
9. Ongoing allergen immunotherapy or plans to begin such therapy during the study period. The last dose of immunotherapy must have been taken at least 6 months prior to inclusion

10. History of chronic alcohol or drug abuse within 12 months of the enrolment visit
11. Perturbation of usual sleep pattern except due to asthma symptoms (eg, night shift workers)
12. Breast feeding, pregnancy or intention to become pregnant during the course of the study
13. DLco \leq 60% of the lower limit of normal
14. Changes in chest X-ray suggesting clinically significant parenchymal disease other than asthma (further on X-ray in Section 5.2.6)
15. Any clinically significant abnormal findings in physical examination, vital signs, dECG, haematology, clinical chemistry, or urinalysis, which in the opinion of the Investigator, may put the patient at risk because of his/her participation in the study, or may influence the results of the study, or the patient's ability to complete entire duration of the study
16. Receipt of live attenuated vaccines within 30 days prior to the date of randomization and during the study including the follow-up period (Receipt of inactive/killed vaccinations (e.g., inactive influenza) is allowed)
17. Major surgery within 8 weeks prior to the enrolment visit, or planned in-patient surgery or hospitalization during the study period
18. Involvement in the planning and/or conduct of the study (applies to both AstraZeneca staff and/or staff at the study site)
19. Previous randomisation in the present study
In addition, any of the following is regarded as criteria for exclusion from the genetic research:
20. Previous bone marrow transplant
21. Whole blood transfusion within 120 days of the date of genetic sample collection

Procedures for withdrawal of incorrectly enrolled patients see Section 3.4.

3.3 Enrolment and randomization

Investigator(s) should keep a record, the patient screening log, of patients who entered pre-study screening.

The Investigator(s) will:

1. Obtain signed informed consent from the potential patient before any study specific procedures are performed.
2. Assign potential patient a unique enrolment number, beginning with 'E#'.
3. Determine patient eligibility. See Section 3.4.
4. Assign eligible patient unique randomisation code (obtained via the IxRS)

If a patient withdraws from participation in the study, then his/her enrolment/randomisation code cannot be reused. Patients can only be randomized into the study once.

Randomisation codes will be assigned strictly sequentially as patients become eligible for randomisation.

3.4 Procedures for handling incorrectly enrolled or randomized patients

Patients who fail to meet the eligibility criteria should not, under any circumstances, be enrolled or receive study medication. There can be no exceptions to this rule. Patients who are enrolled, but subsequently found not to meet all the eligibility criteria must not be randomized or initiated on treatment, and must be withdrawn from the study.

Where a patient does not meet all the eligibility criteria but is randomized in error, or incorrectly started on treatment, the Investigator should inform the AstraZeneca study physician immediately, and a discussion should occur between the AstraZeneca study physician and the investigator regarding whether to continue or discontinue the patient from treatment. The AstraZeneca study physician must ensure all decisions are appropriately documented.

3.5 Methods for assigning treatment groups

The randomization scheme for this study will be generated by the biostatistics group at AstraZeneca or designee. This will be done using AZRand system. Randomization will be performed through a centralized interactive voice and web response system (IxRS). Patients will be block randomized 1:1 to either placebo or AZD1419, with no stratification.

3.6 Methods for ensuring blinding

The study is double-blind; patients, study site personnel and AZ personnel involved in the evaluation of the data must be kept blinded.

Packaging and labelling of study drug will be performed in a way that ensures blinding.

The following personnel will have access to the randomisation list:

- AstraZeneca Supply Chain
- IxRS vendor
- CRO for drug distribution (Fisher)

Randomization will occur after eligibility has been confirmed based on all study inclusion and exclusion criteria.

If all eligibility criteria are met, blinded personnel will contact the centralized interactive voice and web response system (IxRS) to receive a randomization number and treatment assignment.

3.7 Methods for unblinding

Individual treatment codes, indicating the treatment randomisation for each randomised patient, will be available to the Investigator(s) or pharmacists from the IxRS. Routines for this will be described in the IxRS user manual that will be provided to each centre.

The treatment code should not be broken except in medical emergencies when the appropriate management of the patient requires knowledge of the treatment randomisation. The Investigator documents and reports the action to AstraZeneca, without revealing the treatment given to patient to the AstraZeneca staff.

AstraZeneca retains the right to break the code for SAEs that are unexpected and are suspected to be causally related to an investigational product and that potentially require expedited reporting to regulatory authorities. Treatment codes will not be broken for the planned analyses of data until all decisions on the evaluability of the data from each individual patient have been made and documented.

3.8 Restrictions

The following restrictions are applied during the trial or as indicated below:

- Patients should abstain from donating blood and plasma during the study
- Anti-IgE therapy
- Allergen immunotherapy
- Male patients should refrain from fathering a child or donating sperm during the treatment and until 3 weeks following the last dose
- WOCBP using hormonal contraceptives should abstain from use of any medication with CYP3A4 enzyme inducing properties, (eg, fenytoin, fenobarbital, primidon, karbamazepin, oxkarbazepin, rifampicin, rifabutin, ritonavir, topiramate, felbamate and herbal medicines such as St John's Wort) from Visit 1 until 1 month after last dose of IMP.
- ICS, LABA and SABA are the only asthma medications allowed in the study

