During the dosing period the patients' controller medication (ICS + LABA) will be gradually reduced and discontinued. There is a risk of asthma worsening during the study due to this withdrawal design. SABA will be allowed and should be used as needed during the whole study. Patients are required to be well controlled in their asthma ($ACQ-5 \leq 0.75$) at time of randomization and are closely monitored on a daily basis with regards to asthma symptoms, reliever use and lung function (PEF), captured in an ePRO device, during and after the withdrawal period. An automatic asthma action plan will be embedded in the ePRO device and upon worsening of asthma control, i.e. not being adequately controlled as indicated by $ACQ-5 \geq 1.5$, or reduction in PEF and/or increase in rescue medication beyond the set limits the patient will be prompted to resume his/her regular ICS+ LABA controller medication and an alert will be sent to the site (see Section 5.3). With these precautions a gradual worsening of asthma will be detected and the endpoint criteria for reduced asthma control are set so that ICS+LABA can be resumed without undue delay and without risk for patients.

No reproductive toxicology data are available for AZD1419. However, in multiple dose toxicity studies no effects on reproductive organs were observed in either mice or cynomolgus monkeys. Women of childbearing potential will be allowed in the present study provided that contraceptive methods are used as described in this Clinical Study Protocol.

Although the systemic exposure of AZD1419 is expected to be low, systemic Type 1 cytokines (e.g. IFN- α) produced as a result of target engagement may be harmful for an unborn child or lead to spontaneous abortion and the Investigator needs to stress the importance of complying with the contraceptive requirements to Women of Child Bearing Potential.

Women who are breastfeeding, pregnant (verified by urine dipstick pregnancy test) or intends to become pregnant during the study are not allowed to be included.

Pregnancy tests and check of contraceptive compliance will be performed during the treatment. Use of CYP3A4 inducing drugs that may reduce effect of hormonal contraceptives are not allowed.

Patients with asthma may have a potential benefit from treatment as described in the introductions section. With the mitigations and monitoring implemented in the study the overall benefit/risk for the trial patients is judged acceptable.

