6.6.2 Paternal exposure

Male patients should refrain from fathering a child or donating sperm during the treatment and until 1 month following the last dose of IMP.

Pregnancy of the patient's partners is not considered to be an adverse event. However, the outcome of all pregnancies (spontaneous miscarriage, elective termination, ectopic pregnancy, normal birth or congenital abnormality) should if possible be followed up and documented. To capture information about a pregnancy from the partner of a male patient, the male patient's partner consent must be obtained to collect information related to the pregnancy and outcome;

the male patient should not be asked to provide this information. A consent form specific to this situation must be used.

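### Protocol 3.8 ends the restriction on fathering a child or donating sperm 3 weeks after the last dose; 6.6.2 ends the same restriction at 1 month

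*Protocol*

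**What the plan says.** Protocol 3.8, in the list of restrictions that apply during the trial, states: "Male patients should refrain from fathering a child or donating sperm during the treatment and until 3 weeks following the last dose".

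Protocol 6.6.2, in the chapter on safety reporting, states: "Male patients should refrain from fathering a child or donating sperm during the treatment and until 1 month following the last dose of IMP".

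Three other provisions set a post-dose period for preventing pregnancy:

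- Inclusion criterion 7 (Protocol 3.1) requires men to be surgically sterile or to use a barrier method with spermicide "from the first dose of the IMP and until 1 month after the last dose of the IMP to prevent pregnancy in a partner".
- Protocol 3.1.1 has women continue birth control for 1 month after the last dose, and has the male partner use a condom from randomization and "for 1 month after the last dose of inhaled AZD1419/matching placebo to prevent pregnancy".
- In 3.8 itself, the bullet directly below the one at issue bars CYP3A4 inducers for women on hormonal contraceptives "from Visit 1 until 1 month after last dose of IMP".

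**The concern.** One safety instruction appears twice with two different end points. Section 3.8 is a natural place for site staff to look up what a patient may not do, whereas 6.6.2 sits among the rules for reporting pregnancies. A site that relied on 3.8 alone could tell a man he was free to donate sperm or father a child while 6.6.2 still forbade it.

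Little else would catch the error. Protocol Table 1 limits the check of contraceptive history and compliance to women of childbearing potential, and 3.1.1 likewise asks those women to confirm compliance. The documents describe no equivalent check for men, so male patients depend on this instruction being right. Protocol 1.3 also says that AZD1419 has no reproductive toxicology data, which is a reason for the sponsor to apply its chosen period consistently.

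**Working it through.** The plan gives no calculated figure to reproduce here. The check is a comparison of texts followed by simple day counts.

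**Comparison**

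| Provision | What it covers | End of period after last dose |
|---|---|---|
| 3.8, male bullet | Fathering a child, sperm donation | 3 weeks |
| 6.6.2 | Fathering a child, sperm donation | 1 month |
| 3.1, criterion 7 | Male contraception | 1 month |
| 3.1.1 | Women's birth control; condom use by male partner | 1 month |
| 3.8, CYP3A4 bullet | Protection of hormonal contraception | 1 month |

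The first two rows match in population, activities and starting event (the last dose). Only the end point differs. No wording confines either period to a particular dose, subgroup or activity. The precedence rule in Protocol 9.2.2 ranks the protocol against the Clinical Study Agreement, so it does not settle a conflict between two protocol sections. Four of the five rows say 1 month, which identifies 3 weeks as the value to correct.

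**Length of the gap**

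- 3 weeks = 3 × 7 = 21 days.
- 1 month = 28 to 31 days (assumption: calendar month).
- Gap = 28 − 21 = 7 days to 31 − 21 = 10 days.

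**Where it falls for a man who receives all 13 doses**

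- Dose 13 is given at Visit 14 (Week 12). Target day = 1 + 12 × 7 = Day 85, as in SAP Table 6.
- Under 3.8 the restriction ends on Day 85 + 21 = Day 106.
- Under 6.6.2 it ends between Day 85 + 28 = Day 113 and Day 85 + 31 = Day 116.

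These days assume that dose 13 is given on its target day. A man who stops dosing early has the same 7- to 10-day gap, counted from his own last dose.

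**Which activity is left uncovered**

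Criterion 7 requires contraception for the full month but does not mention sperm donation. If 3.8 is followed, conception is still restrained by criterion 7. For sperm donation, the only provision that runs to 1 month is 6.6.2, the one that 3.8 contradicts.

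**The case against.** The mismatch itself is not in dispute. The case on the other side is that it hardly matters.

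- **Conception is already covered.** Criterion 7 binds every man who is not surgically sterile for the same month, and Protocol 3 allows no exceptions to the eligibility criteria. A site would have to overlook that criterion as well as 6.6.2 before 3.8 could shorten contraception. This stands, and it leaves sperm donation as the main practical gap.
- **The risk is small.** Protocol 1.3 reports no AZD1419 detected in plasma at 23.1 mg, about 2.9 times this trial's 8 mg maximum (23.1 / 8 = 2.89), and says that "in multiple dose toxicity studies no effects on reproductive organs were observed in either mice or cynomolgus monkeys". The fetal hazard described there concerns exposure of a pregnant woman, not exposure through a male patient. This also stands: nothing in the documents shows that days 21 to 31 carry a risk. The same section does concede, however, that there are no reproductive toxicology data.
- **The periods are nested.** A site that observes 1 month complies with every provision. True, but a site that reads only 3.8 has no reason to do so.
- **The visit schedule gives little occasion to act on the shorter period.** SAP Table 6 sets Visit 15 at target Day 99 and Visit 16 at Day 113, so no target visit falls between Day 106 and Day 113. This cuts both ways: a man told 3 weeks at an earlier visit would also have no scheduled visit at which to be corrected.
- **The consent text is not available.** What patients were told cannot be judged, so no actual harm can be shown.

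These points limit the consequence. None of them makes the two sentences agree.

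**Conclusion.** The concern holds: 3.8 is wrong as written. It conflicts with 6.6.2 on an operative safety instruction and departs from the 1-month period used for pregnancy prevention elsewhere in the protocol. The gap is 7 to 10 days, with the length of a month as the only assumption. It applies to men able to father a child or donate sperm, and a drug-exposure consequence is possible only in the AZD1419 arm, to which half are allocated under 1:1 randomization. Confidence in the inconsistency is high. It should be corrected because it is a reproductive-safety instruction and the right value is plain from the protocol itself; the likely harm is low. No efficacy analysis is affected.

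**What to change.** In the male-patient bullet of Protocol 3.8, replace the 3-week period with 1 month following the last dose of IMP, so that it agrees with 6.6.2, criterion 7 and 3.1.1. Then confirm that the consent form and any other patient-facing text give 1 month for both conception and sperm donation. The cost is one phrase and that check. Visits, data collection, sample size and analysis are unchanged.
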